Appendix 5. Categorical Classes for Vital Signs of Clinical Concern

Categories for Vital Signs

Systolic BP (mm Hg)	min. < 90	
Systolic BP (mm Hg) change from baseline	max, decrease \leq 30	max, increase \leq 30
Diastolic BP (mm Hg)	min. < 50	
Diastolic BP (mm Hg) change from baseline	max, decrease \leq 20	max, increase \leq 20
Supine pulse rate (bpm)	min. < 40	max. > 120

PFIZER CONFIDENTIAL
Page 31

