6.6.3. Vital Signs

Absolute values and changes from baseline in supine systolic and diastolic blood pressure, oral temperature, and pulse rate will be summarized by treatment in accordance with the sponsor reporting standards. Tables will be paged by parameter. Baseline is as defined in [Section 3.4](#).

Mean changes from baseline for supine systolic and diastolic blood pressure, oral temperature, and pulse rate for each treatment will be plotted against time post-dose. On each plot there will be 1 line for each treatment. Corresponding individual plots of changes from baseline will also be produced for each treatment.

Maximum absolute values and changes from baseline for vital signs will also be summarized descriptively by treatment, using categories as defined in [Appendix 5](#). Numbers and percentages of subjects meeting the categorical criteria will be provided. All planned and unplanned post-dose timepoints will be counted in these categorical summaries. All values meeting the criteria of potential clinical concern will be listed.

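### The four blood-pressure change categories in SAP Appendix 5 point the wrong way: as written, they flag small changes as of clinical concern and exclude large ones

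*SAP*

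**What the plan says.** SAP Appendix 5 carries the title "Categorical Classes for Vital Signs of Clinical Concern". Its blood-pressure change rows have four cells:

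- systolic: "max, decrease \leq 30" and "max, increase \leq 30";
- diastolic: "max, decrease \leq 20" and "max, increase \leq 20".

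The symbol in each is the less-than-or-equal sign. The other rows of the table give absolute limits: systolic below 90, diastolic below 50, and supine pulse below 40 or above 120. There is no upper absolute limit for either blood pressure.

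SAP 6.6.3 puts the table to use: "Maximum absolute values and changes from baseline for vital signs will also be summarized descriptively by treatment", with the Appendix 5 categories. It continues: "Numbers and percentages of subjects meeting the categorical criteria will be provided". All post-dose timepoints count, planned or not. Finally: "All values meeting the criteria of potential clinical concern will be listed". No other section of the protocol or SAP gives a different criterion for a change in blood pressure.

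**The concern.** A category of concern for a largest decrease or increase should pick out changes at or beyond a limit. These cells pick out changes at or within it. That contradicts the title of the appendix, the purpose stated in SAP 6.6.3 and the direction of every other row in the table, all of which flag extremes.

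The cells are an operative rule, because the counts, percentages and listing are defined by them. The trial compares three active doses without a placebo arm, so safety is read largely from tables by dose. If most children at every dose fall in the change rows, those rows say little about whether large blood-pressure changes become more frequent with dose. The listing meant to draw attention to such values would hold the unremarkable ones instead.

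**Working it through.** The SAP states no count or rate for these categories, so there is no figure to reproduce. The check is one of logic, followed by an illustration of size.

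**1. The rule applied as written.** Cut-offs are 30 mm Hg (systolic) and 20 mm Hg (diastolic), from Appendix 5.

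| Largest change, mm Hg | Systolic row, as written | Systolic row, sign reversed | Diastolic row, as written | Diastolic row, sign reversed |
|---|---|---|---|---|
| 0 | counted | no | counted | no |
| 10 | counted | no | counted | no |
| 20 | counted | no | counted | counted |
| 29 | counted | no | no | counted |
| 30 | counted | counted | no | counted |
| 31 | no | counted | no | counted |
| 60 | no | counted | no | counted |

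**2. Can another reading rescue the cells?** The decrease cells could be taken as signed changes (−30 or lower, −20 or lower), but no minus sign is printed. That reading also does nothing for the two increase cells.

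**3. What the absolute rows still catch.** A systolic fall of f mm Hg ends below 90 whenever baseline is below 90 + f.

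- A systolic fall of 31 is caught if baseline is below 90 + 31 = 121.
- A systolic fall of 45 is caught if baseline is below 90 + 45 = 135.
- A diastolic fall of 21 is caught if baseline is below 50 + 21 = 71.
- A rise of any size in either pressure is caught by no absolute row.

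The documents give no baseline pressures, so the number of falls missed cannot be computed.

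**4. How many children the decrease rows would hold.** Inputs from the documents: 63 children in the 12-month part (Protocol 4.1), and nine post-Day-1 visits with vital signs (D4, D8, D15, D29, M2, M3, M6, M9, M12). The visit list is my reading of the Schedule of Activities, whose columns are partly shifted. Assumptions, because the documents give none: normal changes with mean 0, correlation 0.5 between visits, and SD of change 8-15 mm Hg (systolic) or 6-12 mm Hg (diastolic).

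For one visit, the share in the row is Φ(cut-off / SD):

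- systolic: Φ(30/15) = Φ(2.00) = 97.7%, up to Φ(30/8) = Φ(3.75) = 99.99%;
- diastolic: Φ(20/12) = Φ(1.67) = 95%, up to Φ(20/6) = Φ(3.33) = 99.96%.

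For nine visits, the change at visit v was simulated as SD × (√0.5·u + √0.5·e_v), with u and e_v independent standard normal, in 200,000 children. A child is in the row if the largest decrease is at or below the cut-off.

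| Row | SD | In row as written | Of 63, as written | Of 63, sign reversed |
|---|---|---|---|---|
| Systolic decrease | 8 | 99.9% | 63.0 | 0.0 |
| | 10 | 99.0% | 62.3 | 0.7 |
| | 12 | 96.0% | 60.5 | 2.5 |
| | 15 | 87.7% | 55.2 | 7.8 |
| Diastolic decrease | 6 | 99.7% | 62.8 | 0.2 |
| | 8 | 96.0% | 60.5 | 2.5 |
| | 10 | 87.6% | 55.2 | 7.8 |
| | 12 | 77.4% | 48.8 | 14.2 |

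The increase rows are symmetric under this model.

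These shares include children whose pressure never fell, for whom the largest decrease is zero or negative and so meets the printed rule. Correlation 0.5 is what arises when the baseline and nine later readings are independent with equal variance. The baseline is then the lowest of ten readings with probability 1/10. If the program required an actual fall, each share would drop by 10 percentage points, to about 67% (77.4 − 10) through 90% (99.9 − 10).

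**The case against.** **The sign may be a reading error.** The text read here was extracted from a PDF, and one symbol in one small table carries the point. Four identical cells are not four independent confirmations, since a symbol misread once would be misread each time. Nor is every sign in the SAP consistent: Section 3.2 prints the lower age limit as above 2, where Section 2.1 prints at least 2. Against this, the plain less-than and greater-than signs in the same table read sensibly, and the greater-than-or-equal sign reads correctly in SAP 2.1, SAP 5.3.1 and the QTcF criterion in Protocol Appendix 6. The doubt justifies a check of the source page, not dropping the point.

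**Large changes are visible elsewhere.** This stands in good part. A reader might infer that a child with a 45 mm Hg systolic fall goes uncounted and unlisted, or that the safety reporting misses every large change. The documents do not support that. Such a fall is counted and listed through the absolute row unless baseline is 135 or higher. SAP 6.6.3 also requires summaries and individual plots of changes, and SAP 6.6 calls for participant listings of safety endpoints. What remains is the change rows themselves and, for rises, the lack of any other category.

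**The slip is obvious and would be noticed.** That is likely, because a row flagging children with no change looks odd at once. A silent correction would still be an undocumented departure from the SAP. SAP 6.6.3 also refers to sponsor reporting standards, which may hold the right sign but are not part of these documents.

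**Conclusion.** The point holds for the four change cells. As printed, they define the reverse of a category of concern, and nothing else in the documents overrides them. Followed exactly, the change rows and the corresponding listing would hold children with little or no change and leave out those beyond the cut-offs.

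Two stronger readings should be resisted.

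- *That nearly every child would be flagged.* This fits the smaller assumed SDs. At the largest, the share per decrease row is about 88% (systolic) and 77% (diastolic), lower if an actual fall is required. A large majority is what can be said, and the exact share rests on the assumed SDs, correlation and visit count. The direction of the error rests on none of these.
- *That a primary safety endpoint is compromised.* The primary safety endpoint is the frequency and severity of adverse events (Protocol 3, SAP 3.1). Change in vital signs is a secondary safety endpoint (SAP 3.2). No hypothesis, alpha, power or efficacy analysis depends on Appendix 5.

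The error should be corrected before the tables are programmed. Its reach is limited, and it matters most for large rises in blood pressure.

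**What to change.** Check the symbol on the source page of SAP Appendix 5 and against the sponsor reporting standard. If it is printed as read here, change it to greater than or equal to in the four change cells, keeping the SAP's own cut-offs of 30 and 20 mm Hg. Appendix 5 then agrees with its title and with SAP 6.6.3. Record the change in the SAP version history.

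The cost is four symbols and one line of history. No data collection, sample size or protocol text changes. This concerns a reporting category only. No view is taken on whether the cut-offs are clinically right or whether an upper absolute blood-pressure limit should be added.

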Appendix 6. List of Abbreviations

	Term
Abs	absolute
AE	adverse event
ANOVA	analysis of variance
BLQ	below the limit of quantitation
BP	blood pressure
CDARS	Clinical Data Analysis and Reporting System (of US Food and Drug Administration)
CI	confidence interval
CSR	clinical study report
DMC	data monitoring committee
ECG	electrocardiogram
E-DMC	external data monitoring committee
FAS	full analysis set
LLOQ	lower limit of quantitation
LOCF	last observation carried forward
LOD	limit of detection
LS	least-squares
LSM	least-squares mean
MedDRA	Medical Dictionary for Regulatory Activities
MMRM	mixed-effects model with repeated measures
N/A	not applicable
PD	pharmacodynamic(s)
PK	pharmacokinetic(s)
PP	per-protocol
PPAS	per-protocol analysis set
PR interval	time from the beginning of the P wave to the beginning of QRS complex
PT	preferred term

	Term
QRS	a combination of the Q wave, R wave and S wave
QTc	corrected QT
QTcB	corrected QT (Bazzett method)
QTcF	corrected QT (Fridericia method)
RR	respiratory rate
SAE	serious adverse event
SAP	statistical analysis plan
SD	standard deviation
SGS	Statistical Guidance Standards
SOP	standard operating procedure
